3. STUDY DESIGN

This trial is a randomized, controlled, multi-centre clinical trial. The subjects selected 192 children aged 6-16 who had developed high myopia, and divided them into intervention group and control group with 96 cases each. The intervention group was treated with the Eyerising RLRL and single vision spectacle lenses, and the control group was treated with single vision spectacle lenses. Then, we compare the changes of myopia during the observation period between the two groups, and evaluate the safety and effectiveness of the test device.

Subjects will be screened after signing the informed consent form (as early as 7 days before the randomization day). The screening test can use the results of the ophthalmological examination in hospital within 1 week, and subjects enter the group after confirming that they meet the selection conditions. On the day of enrolment, the group is confirmed after consultation with the parents, and determine whether to receive

equipment for treatment based on the results of the grouping. Visits were conducted 30±14 days, 90±14 days, 180±14 days, 270±14 days, and 365±14 days after enrolment.

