3.5 Outcomes

1. Primary Outcome: Change of Axial length (AL, mm) at 12-month follow-up
2. Secondary Outcome: Change of cycloplegic spherical equivalent (SE, D) at 12-month follow-up
3. Optional Indicators:

Changes of uncorrected visual acuity (UCVA), best-corrected visual acuity (BCVA), intraocular pressure, etc.;

Changes of corneal thickness (CT), anterior chamber depth (ACD) and lens thickness (LT);

Observe macula and the structure of fundus around the optic disc;

Observe the choroid/retinal thickness of the fundus;

Compliance index: frequency of equipment uses.

[figure not shown]

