3.6 Study sample size

Sample size calculation

The sample size estimation was conducted assuming an α level of 0.05, 90% power, an annual axial elongation of 0.40 mm with a standard deviation of 0.40 mm over 12 months (based on previous results from our study group), and a 50% treatment effect (reducing axial elongation by 0.20 mm). The required sample size was 86 participants per group, totaling 172 participants. After adjusting for a 10% loss to follow-up, the total sample size was 192 participants.

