5.2 Statistical analysis plan

The intention-to-treat (ITT) population comprised participants randomly assigned to either group. Data from all participants who attended at least one subsequent follow-up visit were included in the analysis, regardless of treatment or follow-up visit compliance. No imputation was used for the missing data. Individuals who switched to other myopia treatment modalities, such as orthokeratology or atropine eye drops, or discontinued the RLRL treatment, were censored. If a participant had only one eye with a SER exceeding -4.0 D, that eye was selected for the statistical analysis. In cases where both eyes were exceeding -4.0 D, the right eye was chosen for the analysis.

Treatment efficacy was assessed using longitudinal mixed models for primary (changes in AL) and secondary (changes in SER and IOP) outcomes at multiple follow-up visits. The mixed effects model was fitted with a random intercept and random slope for the participant, where the group, visit, group-by-visit interaction, baseline age, sex, and baseline AL were fixed effects. Estimated mean treatment differences and corresponding 95% confidence intervals (CIs) were derived from mixed models. UCVA alterations were classified into three categories: decline by two or more lines, stable (within a line), or improvement by two or more lines. The BCVA at the 12-month and baseline was evaluated against the 20/25 standard.

Sensitivity analyses were conducted to assess the treatment effects of therapy in controlling myopia progression, specifically axial elongation and SER progression, across different baseline SER and age groups.

A longitudinal mixed-model analysis was conducted to assess the relationship between treatment efficacy and compliance within the intervention group. Treatment compliance in the intervention group was measured as a percentage of the total number of assigned treatment sessions.

Safety analyses were performed in the ITT population. All adverse events were reported individually. Six ophthalmologists, one from each center, independently scrutinized the OCT scans for potential structural anomalies.

6.MONITORING

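### If the effects of age, sex and baseline AL on axial elongation grow over time, the primary model's single coefficient per covariate recovers only part of the possible adjustment at 12 months

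*Combined protocol and SAP*

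**What the plan says.** Section 3.5 defines the primary outcome as "Change of Axial length (AL, mm) at 12-month follow-up". Section 5.2 analyses it through "longitudinal mixed models for primary (changes in AL) and secondary (changes in SER and IOP) outcomes at multiple follow-up visits". On the random part it says: "The mixed effects model was fitted with a random intercept and random slope for the participant". Besides group and visit, the fixed part is described as "group-by-visit interaction, baseline age, sex, and baseline AL were fixed effects".

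Group is therefore the only term allowed to have a different effect at each visit. Neither section 5.2 nor the shorter analysis text in the abstract adds a covariate-by-visit term or a separate 12-month analysis of covariance. Section 5.2 does not say whether visit is categorical or continuous. Section 3.3 mentions stratified block randomisation but does not name age, sex or baseline AL as a factor, so the model is the only stated place where these variables are balanced.

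**The concern.** Change in AL is zero at baseline by construction. A covariate that predicts the rate of elongation therefore has almost no effect on change at month 1 and its largest effect at month 12. The planned model has to summarise that widening effect in one number. With a random slope in the covariance, generalised least squares takes that number mainly from the early visits, where the variance is small and the covariate has hardly acted. The 12-month part of the effect is left in the random-slope variance.

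Two things are at stake at the primary time point. The standard error of the group difference may be larger than the chosen covariates would allow. A chance difference between arms in age or baseline AL may also be only partly corrected, although the estimate would be reported as adjusted for both.

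**Working it through.** **Inputs from the documents.** Section 3.6 is sized "assuming an α level of 0.05, 90% power", with "an annual axial elongation of 0.40 mm with a standard deviation of 0.40 mm over 12 months" and a reduction of 0.20 mm. It gives 86 per group, 172 in total, and 192 after 10% loss. On timing, section 3 states: "Visits were conducted 30±14 days, 90±14 days, 180±14 days, 270±14 days, and 365±14 days after enrolment". Section 4.2 asks for AL precision below 0.05 mm at follow-up, a rough guide to the residual SD.

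**Assumed, because the documents do not give them.** R² (the share of 12-month variance that the covariates explain), residual SD, intercept SD, intercept-slope correlation, and the shape of the covariate effect over time.

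**Step 1: the plan's own figure.** Two-sided, n = 2(1.960 + 1.282)² × 0.40² / 0.20² = 84.06, so 85 per arm by the normal formula and 86 by the t-test. 172/0.9 = 191.1, so 192. At 86 per arm, SE = 0.40 × √(2/86) = 0.0610, and power = Φ(0.20/0.0610 − 1.96) = 90.6%. The figure reproduces, and it uses the plain SD with no credit for covariates.

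**Step 2: what one shared coefficient recovers.** Let t = (30, 90, 180, 270, 365)/365. Let V be the covariance at these times from random intercept, random slope and residual, scaled so that the 12-month variance is 0.40² = 0.16. For a covariate effect of shape f(t), with f = 1 at 12 months:

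- share of the 12-month effect recovered: `b = 1'V⁻¹f / 1'V⁻¹1`
- share of covariate-explained 12-month variance removed: `1 − (1 − b)²`

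Central case: intercept SD 0.03, residual SD 0.04, no correlation, f = t. The weights `1'V⁻¹ / 1'V⁻¹1` on the five visits are 0.597, 0.445, 0.218, −0.010 and −0.250. So b = 0.597×0.082 + 0.445×0.247 + 0.218×0.493 − 0.010×0.740 − 0.250×1 ≈ 0.009, and the share removed is 1 − 0.991² ≈ 2%.

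**Step 3: range over the assumptions** (intercept SD 0 to 0.10 mm).

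| Covariate effect | Residual SD (mm) | Intercept-slope correlation | Share of explained variance removed |
|---|---|---|---|
| Linear | 0.02 / 0.04 / 0.08 | 0 | 0.5% / 2% / 7-8% |
| Linear | 0.02-0.08 | ±0.5 | −31% to +26% |
| Linear | 0.15 | 0 | 22-24% |
| Linear | 0.15 | ±0.5 | 8-36% |
| Square root of time | 0.02-0.15 | 0 or ±0.5 | 31-68%, about half in the central case |

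A negative share means that the coefficient takes the wrong sign for month 12. For example, b = −0.143 gives 1 − 1.143² = −31%.

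**Step 4: simulation check.** REML fits, 300 trials, 86 per arm, R² = 0.2, central case. The coefficient recovered 1.0% of the 12-month effect. The empirical SE of the 12-month contrast was 0.0572 unadjusted, 0.0571 with main effects and 0.0533 with covariate-by-visit terms. The mean model SE was 0.0603 with main effects and 0.0543 with covariate-by-visit terms. The scenario with residual SD 0.15 mm rests on the algebra only.

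**Step 5: what full adjustment would give.** SD = 0.40 × √(1 − R²), with 86 per arm.

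| Assumed R² | SD (mm) | SE | Power |
|---|---|---|---|
| 0 | 0.400 | 0.0610 | 90.6% |
| 2% | 0.396 | 0.0604 | 91.2% |
| 5% | 0.390 | 0.0595 | 92.0% |
| 10% | 0.379 | 0.0579 | 93.3% |
| 20% | 0.358 | 0.0546 | 95.6% |
| 30% | 0.335 | 0.0510 | 97.5% |

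If main effects remove 2-7% of the explained variance, power at R² of 10-30% is 90.7-91.2%. If they remove half at R² = 20%, the effective R² is 0.20 × 0.5 = 10%, and power is 93.3% instead of 95.6%.

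**Step 6: chance imbalance.** At R² = 0.2, a difference of 0.2 SD in the covariate between arms moves the contrast by 0.2 × √(0.2 × 0.16) = 0.036 mm. With b between 0.002 and 0.04 (linear effect, no correlation), the planned model corrects about 0.0001 to 0.0014 mm of that.

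**The case against.** The strongest reply is that nothing in the primary result is invalid. Main-effect covariates are a legitimate specification, 1:1 randomisation keeps the contrast unbiased, and section 3.6 never counted on adjustment. Chance imbalance is already part of the sampling variance that the confidence interval carries. All of this stands. A reader might infer that the 12-month estimate is biased or that 192 is too few, and the documents support neither.

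The second reply is that the premise is assumed. No section says that younger children progress faster, or that sex or baseline AL predicts elongation. The planned analyses across age and SER groups show interest in such factors but give no association. At R² of 2-5% the most that could be gained is 0.6 to 1.4 points of power. This stands too.

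The third reply concerns a stronger reading, that the adjustment is simply lost. That is true only near the central case. The range in step 3 is wide, and the documents give no variance components with which to choose within it. Any truly constant component of a covariate effect, such as baseline measurement error shared by all change scores, is still adjusted.

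Finally, a reader might extend the argument to SER. The schedule in section 4.3 measures SER after baseline only at months 6 and 12, so the early-visit mechanism was not shown there. The point is confined to AL.

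What remains is that the planned AL model fell short of full adjustment in every growing-effect scenario examined, and that the remedy is cheap.

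**Conclusion.** The concern holds in conditional form, as a worthwhile, near-free improvement, with moderate confidence. The specification is in the text, and the mechanism follows from the random slope once covariate effects on AL change grow with time. How much is lost cannot be fixed from the documents. It ranges from nearly all of the available adjustment (linear effect, small residual error, no correlation) to about half or less (square-root-of-time effect), and under positive intercept-slope correlation the adjustment can go slightly the wrong way. In power terms, the most at stake is the gap between 90.6% and 91-97.5% for an assumed R² of 2-30%. If the covariates explain little, little is lost.

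**What to change.** In the AL model of section 5.2, add age-by-visit, sex-by-visit and baseline-AL-by-visit to the fixed effects. State whether visit is categorical; if it is continuous, use covariate-by-time terms instead. Name the 12-month group difference from that model as the primary estimate.

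The cost is a short change of wording and, with five categorical visits, 3 × (5 − 1) = 12 further parameters, which is affordable with 172 to 192 participants. It needs no new data and no change to the sample size. The covariates for the SER model are a separate question that this check does not settle.

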7) Slit-lamp examination: Slit-lamp examination will be used to examine the anterior segment, lens, vitreous, and fundus, and any abnormalities will be recorded.

8) Optical coherence tomography (optional): SS-OCT fundus image acquisition and data processing: using swept source OCT (DRI OCT-1 Atlantis, Topcon) 9 Line Radial follow-up mode to scan and collect images to obtain fundus pictures and fundus tissue tomographic images. Before the collection, the subjects should be asked to sit still for a while, avoid taking coffee and drinks; during collection, doctors should pay attention to correct the axial magnification; researchers should concentrate on collection time to avoid the influence of the time rhythm fluctuation of choroidal thickness. After the choroidal boundary is automatically segmented by the machine's built-in software,

manual verification and correction are carried out, and the choroidal thickness data of 9 regions of the fovea and the inner, middle and outer rings (upper, lower, nasal, and temporal) are obtained.

2. Follow-up Examinations:

- 1) Questionnaire: A questionnaire on adverse events following the intervention will be administered at each follow-up visit and unexpected visits for children in the intervention group. Children and their parents/guardians will be asked about the side effects, including but not limited to short-term glare, flash blindness, and afterimages.
- 2) Visual acuity: An ETDRS chart (Guangzhou Xieyi Weishikang, Guangzhou, China) with standard illumination will be used to measure distance visual acuity. Visual acuity measurement is performed at a distance of 4 meters. Uncorrected visual acuity will be measured for each follow-up visit, best corrected visual acuity will be measured for the baseline, 6-month and 12-month follow-up visit.
- 3) Ocular biometric measurements via IOLMaster: IOLMaster will be used to measure the axial length of both eyes. Five measurements will be taken for each eye. The axial length measurement will be based on the mean of these five values if the desired precision (<0.05 mm) is achieved.
- 4) Cycloplegia: Cycloplegia will be induced with three drops of 1% cyclopentolate administered at the 0, 5th, and 20th minute to each eye. The light reflex and pupil dilation will be checked after an additional 15 minutes. Dilation and light reflex status will be recorded and full cycloplegia will be justified if the pupil dilates to 6 mm or greater and the light reflex is absent.

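### UCVA change, read at baseline and all five follow-up visits, is planned only as three classes, with no group difference or 95% CI on the measured scale

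*Combined protocol and SAP*

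**What the plan says.** Section 3.5 (Outcomes) has axial length (AL) as primary and cycloplegic refraction as secondary. Its optional indicators include, on one line, "Changes of uncorrected visual acuity (UCVA), best-corrected visual acuity (BCVA), intraocular pressure, etc".

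Section 4.2 specifies an ETDRS chart at 4 metres, which "with standard illumination will be used to measure distance visual acuity". At baseline both uncorrected and best-corrected acuity are taken. Afterwards, "Uncorrected visual acuity will be measured for each follow-up visit", while best-corrected acuity is repeated only at 6 and 12 months. Section 3 sets five follow-up visits: "Visits were conducted 30±14 days, 90±14 days, 180±14 days, 270±14 days, and 365±14 days after enrolment".

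Section 5.2 assigns the model-based analysis as follows: "Treatment efficacy was assessed using longitudinal mixed models for primary (changes in AL) and secondary (changes in SER and IOP) outcomes at multiple follow-up visits". Estimated mean differences and 95% CIs come from those models. UCVA is not among the outcomes named. Its only analysis is: "UCVA alterations were classified into three categories: decline by two or more lines, stable (within a line), or improvement by two or more lines". For these classes the section gives no test, effect measure, confidence interval or visit.

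**The concern.** UCVA is the only acuity measure with a full time course. An ETDRS reading has many levels, even if scored only in whole lines. Sorting the change into three classes treats a loss of two lines like a loss of five, and treats every change in the stable band as no change. This holds even when every eye is assigned to a class, so it is separate from the question of where a change between one and two lines belongs.

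The plan cites no guideline or clinical reason that would make the classes the only analysis. Optional rank does not explain it either: section 3.5 lists IOP beside UCVA, and section 5.2 still gives IOP the mixed model.

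At stake is whether the trial can say by how much UCVA differs between groups, in logMAR, letters or lines, and with what uncertainty.

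**Working it through.** **1. The plan's own figure.** Section 3.6 states its inputs as "assuming an α level of 0.05, 90% power, an annual axial elongation of 0.40 mm with a standard deviation of 0.40 mm" and "a 50% treatment effect (reducing axial elongation by 0.20 mm". The standardised effect is 0.20/0.40 = 0.5. With a two-sided test, n per group = 2(1.960 + 1.282)²/0.5² = 84.1, so 85; the t-based version gives 85.03, rounded up to 86. Then 172/0.9 = 191.1, which gives 192 with equal groups of 96. The plan's 86, 172 and 192 are reproduced. They concern AL; nothing is stated for UCVA.

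**2. Full-scale reference.** A two-sample t-test at one visit with 86 per group, d = 0.5 and two-sided 0.05 has 90.3% power. Using d = 0.5 for UCVA is an assumption borrowed from AL.

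**3. Three classes, same effect.** The documents give no mean or SD for UCVA change, so a range was assumed:
- normally distributed change, SD 0.10, 0.15, 0.20 or 0.25 logMAR;
- mean control worsening 0.05, 0.10, 0.15 or 0.20 logMAR, with the RLRL mean lower by 0.5 SD;
- cut at ±0.20 logMAR (two lines), or ±0.15 if changes are rounded to whole lines.

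This gives 4 × 4 × 2 = 32 scenarios, each simulated.

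Worked example (SD 0.15, control mean 0.10, RLRL mean 0.10 − 0.075 = 0.025, cut 0.20):
- Control: improve Φ(−0.30/0.15) = 0.023; decline 1 − Φ(0.10/0.15) = 0.252; stable 0.725.
- RLRL: improve Φ(−0.225/0.15) = 0.067; decline 1 − Φ(0.175/0.15) = 0.122; stable 0.812 (rounded).

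| Comparison (d = 0.5, 86 per group) | Worked example | All 32 scenarios |
|---|---|---|
| Full-scale change, one visit | 90% | 90% |
| Three classes, ordinal (Wilcoxon) test | 71% | 35–84% |
| Three classes, chi-square | about 62% | 24–75% |

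**4. Analytic cross-check.** The share of information about a mean shift kept by three classes is Σ(φₖ − φₖ₊₁)²/pₖ, where φₖ and φₖ₊₁ are the normal densities at the limits of class k and pₖ is its probability. For mean 0, SD 1 line and cuts at ±1.5 lines, this is 2 × 0.1295²/0.0668 = 0.50. A comparison with 90% power then has Φ(√0.502 × 3.242 − 1.96) = 63%. Over SD 1 to 3 lines and mean change 0 to −2 lines, 50% to 81% of the information is kept, so equal precision needs 1.23 to 1.99 times as many participants. The best symmetric three-class split of a normal variable keeps 81%.

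**5. Smaller effects.** In the worked example with d = 0.2, the full scale has about 26% power and the ordinal test about 17–18%. With d = 0.1 the figures are about 9–10% and 7–8%. The gap in percentage points shrinks, and neither analysis is informative.

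**6. Chart limit.** Readings were capped at an assumed 1.0 logMAR, with baseline mean 0.7, 0.9 or 1.1 (SD 0.25), and change SD, control mean and cut as in the worked example. Full-scale power falls to about 82%, 70% and 48%, and the ordinal test to about 55%, 37% and 21%. Both lose power and the full scale stays ahead. The cap also shrinks the estimated mean difference.

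**The case against.** The strongest objection is that section 5.2 names no test for the classes. If the table is descriptive, which is a natural reading, it has no power to lose, and the percentages above describe tests that the plan does not contain. This stands. What then remains is that no UCVA effect estimate is planned.

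Four further objections:
- **UCVA is optional.** It is not powered, and myopia progression is already estimated on the continuous scale through AL and refraction. This stands and limits the severity. As a reason for leaving UCVA out of the model it is weak, because IOP has the same rank in section 3.5.
- **The effect size is borrowed.** Nothing in the documents supports a 0.5 SD effect on a subjective acuity reading. This stands, so the figures are illustrative.
- **Many eyes may be at the chart limit.** Analysed eyes have at least 4 D of myopia and are read without correction. This partly stands: the limit lowers power and strains a linear model, but in the check it did not favour the classes.
- **The calculation is a single-visit t-test.** No mixed model was fitted, and section 4.2 does not say whether acuity is scored by letter or by line. This stands.

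A reader might infer that the plan has been shown to lose a definite amount of UCVA power against its own mixed model, or that the efficacy conclusions are weakened. The documents support neither: they give no UCVA test, SD or expected effect, and no primary or secondary conclusion rests on UCVA.

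**Conclusion.** The point holds in limited form. As written, section 5.2 yields either no UCVA treatment effect (classes only tabulated) or a comparison that discards information (classes tested). Under the assumed normal model the direction of the loss is consistent; its size is not known. At the borrowed 0.5 SD effect, the full scale is ahead by at least 6 points in every scenario (90.3% against at most 83.8%). With SD 0.15–0.20 and a 0.20 cut it is ahead by about 10–20 points over the ordinal test and 20–30 over chi-square. These margins rest on assumed means and SDs and on a single visit, and they are smaller in points at smaller effects. The AL and refraction analyses are not affected. This is a cheap improvement, desirable rather than essential.

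**What to change.** In section 5.2, add an analysis of change in logMAR UCVA, using the same type of longitudinal mixed model as for AL, with baseline UCVA as a covariate. Report the 12-month group difference with its 95% CI. Keep the three-class table as a descriptive summary.

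The cost is one SAP sentence and one more model run on data already collected, with no extra visits, staff or participants. A small downside is that eyes at the chart limit may skew the distribution and shrink the estimated difference. The number of eyes at the limit should therefore be reported by group beside the estimate.

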8.2 Plan modification

8.3 Informed consent

8.4 Confidentiality

1. ABSTRACT

Basic information on clinical practice of medical devices:

Device Classification: Class II medical devices

Specification Model: RS-200-1A

Date: September 20, 2020

Sponsor: Zuoguan Medical Devices Co., Ltd. at Suzhou Industrial Park

Practice Title

A Randomized, Controlled, Multi-centre Clinical Study on the Effectiveness and Safety of repeated low-level red-light (RLRL) for myopia control in children and adolescents with high myopia

Practice Purpose

A Study on assessing the effectiveness and safety of RLRL for myopia control in children and adolescents with high myopia.

Subject Population

Subject: Children aged 6-16 with at least one eye with myopia of cycloplegic spherical equivalent refraction (SER) at least -4.0 D

Sample size: 192 subjects are planned to be enrolled and assigned to the intervention group or control group according to a ratio of 1:1

Practice Design

Overall design:

This prospective, single-blind, parallel-group, multi-center randomized clinical trial was conducted at six tertiary hospitals. Participants between 6 and 16 years old with at least one eye with a spherical equivalent refraction (SER) of -4.0 D or greater were recruited. The enrolled participants were randomly placed at a 1:1 ratio into

intervention (RLRL treatment plus single-vision spectacles) or control (single-vision spectacles) groups. The participants attended follow-up appointments 1, 3, 6, 9, and 12 months after the baseline evaluation.

Outcomes:

1. Primary Outcome: Change of Axial length (AL, mm) at 12-month follow-up
2. Secondary Outcome: Change of cycloplegic spherical equivalent (SE, D) at 12-month follow-up
3. Optional Indicators:

Changes of uncorrected visual acuity (UCVA), best-corrected visual acuity (BCVA), intraocular pressure, etc.;

Changes of corneal thickness (CT), anterior chamber depth (ACD) and lens thickness (LT);

Observe macula and the structure of fundus around the optic disc;

Observe the choroid/retinal thickness of the fundus;

Compliance index: frequency of equipment uses.

Safety assessment

- ① Sudden vision loss;
- ② Afterimage time over 5 minutes;
- ③ Side effects such as glare, photophobia and flickering;
- ④ Structural damage to retina: tissue disruption or discontinuity, edema, or other abnormalities in the photosensory layer of the SS-OCT images;
- ⑤ Increased intraocular pressure etc.

Participants selection and exclusion criteria:

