3.1 Eligibility criteria

Inclusion criteria

- ① Age 6-16 years old, no gender limit;
- ② Either eye meets the diagnosis of myopic refractive error and the myopia of cycloplegic spherical equivalent refraction (SER) at least -4.0 D, astigmatism 2.0 D or less, anisometropia 3.0 D or less, and best-corrected visual acuity (BCVA) of LogMAR 0.2 or better.
- ③ Have normal thinking and language communication skills, and be able to actively cooperate with the required treatment;
- ④ No contraindications to the treatment of atropine such as acute ocular inflammation, dry eye, keratoconus, diabetes, etc.;
- ⑤ Written informed consent of the guardian and the child.

Exclusion criteria

- ① A history of photosensitivity, glaucoma, glaucoma syndrome, ocular hypertension, and macular pathology or damage in the fundus;
- ② Corneal curvature examination, the average K value of the anterior surface of the cornea is ≥ 45 ;
- ③ Patients with heart, liver, kidney and other systemic diseases and congenital hereditary myopia;
- ④ Patients with chronic eye diseases such as ocular trauma and oblique or surgical eyes, atopic keratoconjunctivitis;
- ⑤ Patients with previous eye diseases such as inverted trichiasis, severe corneal and conjunctival infections;
- ⑥ Patients with neurological diseases and allergies or contraindications to atropine drugs or other therapeutic drugs;
- ⑦ Patients with immune system and systemic diseases such as albinism, psoriasis, nephrotic syndrome, systemic lupus erythematosus, diabetes, etc.;
- ⑧ People with epilepsy, mental disorders and unable to communicate normally;

- ⑨ Those who have previously received other treatments to control the development of myopia, such as the use of anticholinergic drugs such as atropine within 3 months, or participated in other functional frame mirrors, multifocal soft mirrors and other related researchers;
- ⑩ Other situations that the researcher judges are not suitable for participating in the research.

Participant withdrawal or termination

A study investigator will terminate participation in the study for the following reasons:

- 1) The patient receives other myopia control treatments;
- 2) Patients continuously stop using Eyerising equipment for more than 14 days;
- 3) Severe comorbidities or adverse events: patients cannot tolerate light, have obvious eye allergies such as tearing, skin rash, and the after-image time after low-energy laser treatment exceeds 5 minutes;

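### The only stated BCVA analysis, a 20/25 comparison at baseline and month 12, can miss a two-line loss, and no summary of the month-6 BCVA is named

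*Combined protocol and SAP*

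**What the plan says.** Section 5.2 contains one sentence on BCVA: "The BCVA at the 12-month and baseline was evaluated against the 20/25 standard". The sentence before it sets a line-change rule, but for uncorrected acuity only: "UCVA alterations were classified into three categories: decline by two or more lines", with matching categories for stable and improved eyes. The analysis summary in the Abstract adds nothing on BCVA.

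Elsewhere the plan treats BCVA as a measure of change. Section 3.5 lists among its optional indicators "Changes of uncorrected visual acuity (UCVA), best-corrected visual acuity (BCVA), intraocular pressure, etc". Section 4.2 states that "best corrected visual acuity will be measured for the baseline, 6-month and 12-month follow-up visit". Section 3.1 admits eyes with "best-corrected visual acuity (BCVA) of LogMAR 0.2 or better". The safety list in the Abstract includes "Sudden vision loss" without saying how many lines count as loss.

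**The concern.** A comparison with a fixed acuity level records whether an eye is on one side of a line. It does not record how far that eye has moved. Entry is allowed up to logMAR 0.2, so eyes on both sides of 20/25 can enroll. An eye well above the line, or already below it, can lose two lines and keep the same status, while a one-line drift across the cut counts as a change.

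The two-line rule that would catch such a loss is applied to uncorrected acuity, which in eyes of -4 D or worse is dominated by defocus. Corrected acuity removes the defocus and is the better functional signal of retinal harm.

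Month 6 matters for children who leave early. Section 3.1 ends participation for, among other reasons, "Patients continuously stop using Eyerising equipment for more than 14 days" and for afterimages lasting over 5 minutes, and no exit examination is scheduled. For a child who leaves between months 6 and 12, the month-6 value is the only scheduled follow-up BCVA, and a baseline-to-month-12 comparison cannot use it.

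The device is a Class 3R laser that children look into twice a day, and safety is part of the stated purpose. Readers will look for individual loss of corrected vision.

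**Working it through.** **Inputs.** From the documents: the 20/25 comparison at baseline and month 12 (5.2); entry BCVA of logMAR 0.2 or better (3.1); BCVA at baseline, month 6 and month 12 on an ETDRS chart (4.2); 172 children before and 192 after the dropout allowance (3.6). Assumed: 0.1 logMAR per ETDRS line, so two lines = 0.2; and that the 20/25 comparison is a pass/fail threshold.

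**The plan's own figure.** BCVA has no sample size. The 172 used below as a denominator comes from 3.6 and reproduces: a two-sided t-test with difference 0.20 mm, SD 0.40 mm, alpha 0.05 and 90% power gives 85.03, rounded up to 86 per group, or 172. Then 86 / 0.90 = 95.6, rounded up to 96 per group, or 192.

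**Step 1: the cut.** log10(25/20) = 0.097, about the 0.1 line.

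**Step 2: add 0.2 to each eligible starting line and compare with 0.1.**

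| Baseline | After two-line loss | Status at the two visits | Loss visible? |
|---|---|---|---|
| -0.2 | 0.0 | meets, meets | no |
| -0.1 | 0.1 | meets, meets | no |
| 0.0 | 0.2 | meets, fails | yes |
| 0.1 | 0.3 | meets, fails | yes |
| 0.2 | 0.4 | fails, fails | no |

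With the cut at exactly 0.097, only the boundary starts -0.1 and 0.1 swap places; a hidden range remains on each side. At the 0.1 cut, a one-line change from 0.1 to 0.2 alters status.

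**Step 3: illustrative share hidden.** Assume baseline BCVA is normal, cut at 0.2, and the loss is exactly 0.2. Share hidden = P(baseline <= -0.1 or 0.1 < baseline <= 0.2) / P(baseline <= 0.2).

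| Mean | SD 0.06 | SD 0.08 | SD 0.10 |
|---|---|---|---|
| -0.05 | 0.209 | 0.296 | 0.371 |
| 0.00 | 0.095 | 0.206 | 0.301 |
| 0.05 | 0.204 | 0.274 | 0.331 |

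For a loss of exactly 0.3, replace -0.1 by -0.2: the range becomes 0.012 to 0.266.

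**Step 4: month 6.** Section 3.6 states: "After adjusting for a 10% loss to follow-up, the total sample size was 192 participants". The allowance is 192 - 172 = 20 children. The timing of loss is not given, so anywhere from 0 to 20 of these would have month 6 as their only follow-up BCVA.

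**Step 5: false flags from a 0.2 rule.** For an unchanged eye with an assumed test-retest difference SD s, P(flag) = 1 - Phi(0.2/s). "Either visit" is 2P minus the joint probability, with correlation 0.5 between the two changes because they share a baseline.

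| s | Per visit | of 172 | Either visit | of 172 |
|---|---|---|---|---|
| 0.05 | 0.00003 | 0.0 | 0.00006 | 0.0 |
| 0.07 | 0.002 | 0.4 | 0.004 | 0.7 |
| 0.10 | 0.023 | 3.9 | 0.041 | 7.1 |

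These are for one eye per child; counting either eye raises them.

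**The case against.** BCVA is an optional indicator, neither primary nor secondary, and a threshold and a line-loss count are two summaries of the same readings. Nothing in the plan is contradicted, and no efficacy estimate is biased. That stands.

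A reader might infer that loss of vision would go undetected. The documents do not support this. Adverse events are recorded at every follow-up visit and reported individually, slit-lamp and OCT are done at months 6 and 12, and six ophthalmologists read the OCT scans independently. OCT and slit-lamp do not depend on symptoms. None of these sets a BCVA threshold, however, and the side-effect questionnaire in 4.2 is specified for the intervention group only, whereas BCVA is measured in both arms by examiners described as blinded.

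A reader might also infer that children who leave before month 12 are dropped from the analysis. Section 5.2 says otherwise: it includes everyone with at least one follow-up visit, whatever their compliance. What is missing is a named month-6 BCVA summary. The same section censors children who switch or stop treatment, and it does not say whether that reaches safety measures such as BCVA.

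The hidden shares are soft. They rest on an assumed baseline distribution and are conditional on a loss of a given size. The number of children affected could be zero.

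**Conclusion.** The point holds as a gap in how measured BCVA is summarized. Section 5.2 states one BCVA analysis. Read as a threshold, it can miss a two-line loss from about -0.1 or better, or from between 0.1 and 0.2, and it names no month-6 summary. If the 20/25 sentence was meant in another way, 5.2 should say so.

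The size cannot be fixed from the documents. The 10-37% range (1-27% for three lines) is illustrative and should not be read as the proportion of children harmed or overlooked. The 20 children in the dropout allowance are a planning figure, not a ceiling. Sample size, power and the axial-length analysis are unaffected. This is a worthwhile improvement to safety reporting, not an error that undermines the trial.

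**What to change.** In 5.2, keep the 20/25 comparison and add:

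*Change from baseline in BCVA (logMAR) is reported at months 6 and 12 by arm, with the number and percentage of children losing 0.2 logMAR or more at each visit and at either visit, with exact 95% CI, for the study eye and for either eye. All measured values are included for this safety summary, including month-6 values of children without a month-12 visit and values after censoring for efficacy.*

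The either-eye count is needed because 5.2 analyzes one eye per child while the device treats both. It requires BCVA to be recorded in both eyes, which 4.2 does not spell out for acuity; one added phrase there would settle it.

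Cost: one paragraph and a few table rows. No visit or type of test is added. If ethics approval is in place, section 8 requires the change to be submitted for re-approval. The fix adds no reading for a child who leaves before month 6.

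Downside: some flagged losses will be noise, 0-4 of 172 per visit and 0-7 at either visit for one eye, and more when either eye counts. Reporting both arms shows that background rate. The intervals will also be informative only to a degree: with no losses among 86 RLRL children, the exact two-sided 95% upper limit is 1 - 0.025^(1/86) = 4.2%.
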